6.3 STATISTICAL ANALYSIS.....	13
7 DATA.....	14
7.1 AUTHORSHIP ELIGIBILITY GUIDELINES AND ANY INTENDED USE OF PROFESSIONAL WRITERS.....	14
7.2 DATA PROTECTION	14
7.3 DATA RETENTION	15
8 APPENDICES	16
APPENDIX 1 – SCHEDULE OF PROCEDURES.....	16

KEY TRIAL CONTACTS

Chief Investigator

[name]

NEAT ID Foundation

Registered address: [name],
Belgium

Administrative office: [name]

[contact]

Sponsor

NEAT ID Foundation (NEAT ID)

Registered address: [name],
Belgium

Administrative office: [name]

Project Management

909-REM Project Manager

Research Organisation (KC) Ltd. (ROKC)

[name]

[contact]

Data Management

Clinical Informatics Team

Research Organisation (KC) Ltd. (ROKC)

[name]

STUDY SYNOPSIS

Full study Title	A Multi-centre, Multi-country Retrospective Cohort Study to Evaluate the Clinical Outcomes in Adults with COVID-19 who have been treated with Remdesivir.	
Short title/Acronym	NEAT ID 909REM	
Clinical Phase	IV	
Trial Design	A multi-centre, multi-country retrospective cohort study	
Name of Non-Investigational Product	Remdesivir	
Trial Participants population	At least 450 cases	
Planned Sample Size	At least 450 cases, at least 450 controls (if required, controls will be included in Part 2)	
Eligibility Criteria	
Cases
 
All Adult participants with COVID-19 confirmed by PCR who meet the following criteria:
 
 1. Hospitalised after August 31st 2020 2. Received Remdesivir (RDV) at any time during hospitalisation 	
Indication	COVID-19	
Number of sites	up to 20	
Objectives	
Primary The primary objectives of this study are to assess the clinical course and outcome of adults with COVID-19 who have been treated with Remdesivir assessed by:
 
 1. All-cause mortality at Day 28; 2. duration of hospitalisation 	
Secondary The secondary objectives are to assess the clinical course and outcome of adults with COVID-19 who have been treated with Remdesivir with respect to the following:
 
 1. a 7-point ordinal clinical status scale on Day 7 and Day 14 2. timing (from first symptoms and from hospitalisation) and duration of use of Remdesivir 3. clinical severity at Day 7, 14, 28 as assessed by the NEWS 2 score 4. clinical status as assessed a 7-point ordinal scale on Day 28 (or at last observation if discharged or died)

		
prior to this time point) in those still hospitalised after Day 14.
 
 5. SpO₂ > 94% on room air on day 7, 14 and 28 6. duration and type (low versus high flow) of oxygen therapy (days) 7. admitted to ICU (yes versus no) 8. Number of days spent on ICU/ITU 9. use of mechanical ventilation/ECMO (extracorporeal membrane oxygenation); start and stop dates 10. re-admission with COVID-19 complications or recurrence within 28 days of discharge and outcome (discharged or deceased)
Criteria for Evaluation	
Primary
 
 1. All-cause mortality at day 28 2. Clinical status assessed by a 7-point ordinal scale on Day 14 or at last observation if discharged or died prior to this time point, where the 7-point ordinal scale is defined as: 
 1. Death 2. Hospitalised, on invasive mechanical ventilation or ECMO 3. Hospitalised, on non-invasive ventilation or high flow oxygen devices 4. Hospitalised, requiring low flow supplemental oxygen 5. Hospitalised, not requiring supplemental oxygen - requiring ongoing medical care (COVID-19 related or otherwise) 6. Hospitalised, not requiring supplemental oxygen - no longer requires ongoing medical care 7. Not hospitalised 	
Secondary
 
 1. Proportion of clinical improvement at Day 14, defined as a ≥ 2-point improvement from Day 1 on a 7-point ordinal scale 2. Timing and duration (days) of Remdesivir 3. Severity of disease on Day 7, Day 14 and Day 28 based on NEWS 2 score 4. Clinical status assessed by a 7-point ordinal scale on Day 28 (or at last observation if discharged or died prior to this time point) in those still Hospitalised after day 14. 5. Time to SpO₂ > 94% on room air (number of days when evaluation made on day 7, 14 or 28) 6. Duration of oxygen therapy (total days) 7. Admitted to ICU 8. Need for and time on mechanical ventilation/ECMO of hospitalisation 9. Duration of hospitalisation

FUNDING AND SUPPORT

FUNDER(S)	COLLABORATORS/KEY CONTRIBUTORS
Gilead Sciences [name]	NEAT ID Foundation Registered address: [name], Belgium Administrative office: [name]
	Research Organisation King's Cross (KC) Ltd. [name]
	[name] (Director) INSERM Centre de méthodologie et de gestion (CMG) Equipe 3 Epidémiologie clinique de l'infection à VIH : stratégies thérapeutiques et comorbidités Institut Pierre Louis d'Epidémiologie et de Santé Publique Sorbonne Université, [name]

2. OBJECTIVES AND OUTCOME MEASURES/ENDPOINTS

2.1 Primary objective

The primary objectives of this study are to assess the clinical course and outcome of adults with COVID-19 who have been treated with Remdesivir assessed by:

1. all-cause mortality at Day 28
2. duration of hospitalisation

2.2 Secondary objectives

The secondary objectives are to assess the clinical course and outcome of adults with COVID-19 who have been treated with Remdesivir with respect to the following:

1. a 7-point ordinal clinical status scale on Day 7 and Day 14
2. timing (from first symptoms and from hospitalisation) and duration of use of Remdesivir
3. clinical severity at Day 7, 14, 28 as assessed by the NEWS 2 score
4. clinical status as assessed a 7-point ordinal scale on Day 28 (or at last observation if discharged or died prior to this time point) in those still hospitalised after Day 14.
5. SpO₂ > 94% on room air on day 7, 14 and 28
6. duration and type (low versus high flow) of oxygen therapy (days)
7. admitted to ICU (yes versus no)
8. number of days spent on ICU/ITU
9. use of mechanical ventilation/ECMO (extracorporeal membrane oxygenation); start and stop dates
10. re-admission with COVID-19 complications or recurrence within 28 days of discharge and outcome (discharged or deceased)

2.3 Primary Criteria for Evaluation

1. All-cause mortality at day 28
2. Clinical status assessed by a 7-point ordinal scale on Day 14 or at last observation if discharged or died prior to this time point, where the 7-point ordinal scale is defined as:
 1. Death
 2. Hospitalised, on invasive mechanical ventilation or ECMO
 3. Hospitalised, on non-invasive ventilation or high flow oxygen devices
 4. Hospitalised, requiring low flow supplemental oxygen
 5. Hospitalised, not requiring supplemental oxygen - requiring ongoing medical care (COVID-19 related or otherwise)
 6. Hospitalised, not requiring supplemental oxygen - no longer requires ongoing medical care
 7. Not hospitalised

2.4 Secondary Criteria for Evaluation

1. Proportion of clinical improvement at Day 14, defined as a \geq 2-point improvement from Day 1 on a 7-point ordinal scale
2. Timing and duration (days) of Remdesivir
3. Severity of disease on Day 7, Day 14 and Day 28 based on NEWS 2 score
4. Clinical status assessed by a 7-point ordinal scale on Day 28 (or at last observation if discharged or died prior to this time point) in those still hospitalised after day 14.
5. Time to SpO₂ $>$ 94% on room air (number of days when evaluation made on day 7, 14 or 28)
6. Duration of oxygen therapy (total days)
7. Admitted to ICU
8. Need for and time on mechanical ventilation/ECMO of hospitalisation
9. Duration of hospitalisation

3 TRIAL DESIGN

This is a multi-centre, multi-country retrospective cohort study. At least 450 COVID-19 cases from up to 20 participating study sites who meet all eligibility criteria will be included in the analysis. Deidentified data will be extracted from electronic medical record (EMR) databases, clinical registries, case series or additional sources from participating sites and countries, and then entered into a structured e-CRF system. In addition, each site/country will be surveyed to determine the local standard of care therapy for COVID-19 infection and to determine if standard protocols were/are in place for the use of Remdesivir and if/how the protocols changed over time.

Number of Sites and Subjects Planned

Up to 20 centres with 450 cases of Covid-19 treated with at least one dose of Remdesivir

Target Population

Adults with COVID-19 diagnosed and treated with Remdesivir after Aug 31st 2020.

Comparator group-(Part 2)

Part 2, which is collecting data on non-RDV treated controls, will only be initiated, if required, and once data from Part 1, the cases, is collected and analysed. Matching criteria will be detailed in a study management document.

4 ELIGIBILITY CRITERIA

4.1 Inclusion criteria

Diagnosis and Main Eligibility Criteria - Cases(Part 1)

All Adult participants with COVID-19 confirmed by PCR who meet the following criteria:

1. Hospitalised after August 31st, 2020
2. Received at least one dose of Remdesivir (RDV) at any time during hospitalisation

Diagnosis and Main Eligibility Criteria –Controls (Part 2)

Adult participants with COVID-19 confirmed by PCR who meet the following criteria:

1. Hospitalised after August 31st 2020

4.2 Exclusion criteria

Exclusion Criteria – Cases (Part 1)

1. Received Remdesivir as part of a clinical trial, compassionate use or expanded access program
2. Received Remdesivir prior to this admission at any other health facility than the research sites and whose health records are available.

Exclusion Criteria – Controls (Part 2)

1. Received Remdesivir at any time during hospitalisation

5 TRIAL PROCEDURES

Only real-world retrospective data will be used for this study. Deidentified retrospective data will be extracted at each clinical site from source data. No personal identifiable data will be transmitted to NEAT ID. Data will be extracted/transcribed in to the eCRF database with standard formatting from electronic medical record (EMR) databases, clinical registries, case series or additional sources from sites/ countries. The data elements will be extracted/transcribed from source data according to the following schedule. Mechanisms to ensure data quality and integrity will be deployed as per applicable standard operating procedures.

	Day1 (Hospital Admission)	Day7 (+/- 1 day) and Day14 (+/- 2 days) / last observation if discharged or died prior to these time points.	Day 28 or last observation after Day 14 if discharged or died prior to this time point.
Medical History ^a	X		
Pregnancy test	X		
HIV test	X		
Vital Signs ^b	X	X	X
Laboratory Testing ^c	X	X	X
Oxygenation ^d	X	X	X
Clinical Status ^e	X	X	X
Other Treatments for COVID-19 ^f	X	X	X
NEWS SCORE ^g	X	X	X

- a. Focused medical history and also the following information (e.g. demographics including ethnicity, baseline characteristics including DM, CV disease and COPD)
- b. SpO₂, body temperature, body weight and height on admission
- c. Includes white blood cell count, creatinine, total bilirubin, ALT, AST at admission Day 7 and day 14 or at discharge if before day 14, radiographic findings at baseline and as available and SARS-CoV-2 pcr, antigen and/or antibody testing.
- d. Includes oxygen supplementation: room air, low flow O₂ (L/min and %), high flow O₂ (L/min and %), non- invasive

positive pressure ventilation (FiO2 or %), mechanical ventilation (FiO2 or %), ECMO (extracorporeal membrane oxygenation)

- e. The ordinal scale is as: 1. Death, 2. Hospitalised, on invasive mechanical ventilation or ECMO, 3. Hospitalised, on non-invasive ventilation or high flow oxygen devices, 4. Hospitalised, requiring low flow supplemental oxygen, 5. Hospitalised, not requiring supplemental oxygen - requiring ongoing medical care (COVID-19 related or otherwise), 6. Hospitalised, not requiring supplemental oxygen - no longer requires ongoing medical care, 7. Not hospitalised
- f. These include corticosteroids, anticoagulants, azithromycin/other antibiotics, anti-inflammatory agents (e.g. Tocilizumab), investigational agents (eg hydroxychloroquine) and immunotherapies such as convalescent plasma and monoclonal antibodies.
- g. NEWS 2 score is based on Respiration rate (per minute), SpO2 (%) Air or oxygen. Systolic blood pressure (mmHg), Pulse (per minute) Consciousness, Temperature (°C)

6 STATISTICS AND DATA ANALYSIS

6.1 Subject population

Target Population

Adults with COVID-19 diagnosed and treated with Remdesivir after Aug 31st 2020.

Comparator group

Part 2, which is collecting data on controls, will only be initiated, if required, and once data from Part 1, the cases, is collected and analysed.

The matching criteria for controls, who were given standard of care but not Remdesivir, and who were admitted in a 2 week time window of the cases will be determined once the target population of Part 1, the cases, data has been collected and analysed.

6.2 Study size

This is a non-interventional, observational study where no formal samples size calculation is to be performed. It is anticipated that at least 450 adults with COVID-19 and treated with Remdesivir could be recruited across centres from NEAT ID Network. In addition, 450 other adults with COVID-19 treated with standard of care (control group) will be recruited if needed.

6.3 Statistical analysis

Summary statistics will be generated for the cohort overall and by disease severity at baseline (2 vs 3/4 vs 5). For categorical variables, numbers and percentages of participants will be reported including the 95% confidence intervals. For continuous variables, mean, standard deviation (SD), minimum, first and third quartile (Q1, Q3), median, maximum and 95% confidence intervals will be calculated, together with the total number of observations and the number of missing values. Descriptive statistics will summarize demographics and baseline characteristics. Mortality rate (all causes) at day 28 and its associated 95% confidence interval will be calculated using Kaplan-Meier estimates.

The analysis population will be consisted of all enrolled participants with data available at baseline.

We will assess factors associated with clinical status at day 14 using proportional odds models and factors associated with survival at day 28 using Cox proportional hazards models. For continuous variables, the decision to treat the variable as a continuous or categorical variable (as tertile) will be based on the lowest Akaike information criterion value for the corresponding univariable analysis. Variables achieving $P < 0.10$ in univariable analysis will be retained for the multivariable analysis.

The following variable will be assessed:

- Participating country
- Age group: < 65 vs ≥ 65 years
- Sex at birth: female vs male
- Geographic origin: European vs Sub-Saharan Africa vs. other
- Baseline clinical status (2 vs 3/4 vs 5)
- Body mass index at baseline (<18.5 vs 18.5-25; 25.01-30 vs >30 kg/m²)
- Diabetes at baseline (yes vs no)
- High blood pressure at baseline (yes vs no)
- Time from symptoms onset and date of treatment start (<7 days vs ≥ 7 days)

Secondary endpoints as well as the effect of remdesivir relative to the control group (if Part 2 is performed) will be assessed using appropriate statistical methods for non-randomized cohorts. All details of the analyses will be included in the Statistical Analysis Plan (SAP).

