8.1 Primary Efficacy Analysis

Primary endpoint	
 Occurrence of death within 28 days
Analysis population	
 Full population analysis
Descriptive statistics and graphical representation	
 Data will be summarized with proportion and 95% confidence interval globally and according to disease severity at baseline (ORDSC score 2 vs 3-4 vs 5) LogRank test will be used to compared the 3 groups P-values will be two-tailed with a significant level at 5%. Kaplan-Meier curves will be plotted
Statistical analysis	
Kaplan-Meier estimates will be used to calculate the proportions and the 95% confidence intervals
 
Time to death will be defined as the time between the date of hospitalization and the date of death or discharge from hospital or last observation
 
Participant with missing clinical status or alive at day 28 will be censored at the date of last observation

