Appendix

Table 1: Baseline characteristic of participants and according to the disease severity at baseline

		Ordinal Scale Category at baseline Overall and by disease severity				
		Total N=xxx	ORDSC score 2 N=xxx	ORDSC score 3-4 N=xxx	ORDSC score 5 N=xxx	P- value
Age (years), median (IQR)						
Gender, n (%)		Male				
		Female				
Pregnant women, n(%)						
Ethnicity, n(%)		White caucasian				
		White mixed				
		Asian				
		Black				
		African				
		Caribbean				
		Other				
Geographic origin, n(%)						
		European				
		Other				
Body mass index (BMI, kg/m²), median (IQR)						
		Undeweight ((<18.5 kg/m ²), n(%)				
		Normal (18.5-25 kg/m ²)				
		Overweight (25.01-30 kg/m ²)				
		Obese (>30 kg/m ²)				
Comorbidities, n(%)						
		Cardiovascular Disease excluding Hypertension				
		Diabetes at baseline				
		Cardiovascular Disease excluding Hypertension				
		Hypertension				
		Asthma				
		COPD				
		Severe renal disease				
		Liver disease				
		HIV infection				
		Chemo/radiotherapy for cancer				
		Receiving Immuno-Suppressive Agent (Not for Cancer)				
		Dementia				
Biological parameters						
White blood cells (10 ¹² /L), median (IQR)						
ALT (U/L) , median (IQR)						
AST (U/L) , median (IQR)						
Total Bilirubin (umol/L) , median (IQR)						
Creatinine (umol/L) , median (IQR)						

Creatinine clearance (eGFR) (mL/min), MDRD method, median (IQR)					
Virological results					
	Positive PCR test, n(%)				
	CT value, median (IQR)				
Specimen type, n(%)					
	Nasopharyngeal swab				
	Oropharyngeal swab				
	Other				
Imaging results, n(%)					
	Normal				
	Abnormal				
	Unknown				
Presence of Pulmonary Infiltrates, n(%)					
Imaging Method, n(%)					
	X-Ray				
	CT Scan				
	Other				
Clinical status - Ordinal Scale, n (%)					
	2 - Hospitalized, on invasive mechanical ventilation or ECMO				
	3 - Hospitalized, on non-invasive ventilation or high flow oxygen devices				
	4 - Hospitalized, requiring low flow supplemental oxygen				
	5 - Hospitalized, not requiring supplemental oxygen - requiring ongoing medical care (COVID-19 related or otherwise)				
Temperature (°C), median (IQR)					
	Systolic Blood Pressure (mmHg), median (IQR)				
	Pulse Rate (per minute), median (IQR)				
SpO2 (%), median (IQR)					
Supplemental oxygen, n (%)					
	Room Air				
	Low Flow O2				
	High Flow O2				
	Non-Invasive Positive Pressure Ventilation				
	Mechanical Ventilation				
	ECMO (Extra-Corporeal Membrane Oxygenation)				
Consciousness, n(%)					

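### Baseline categories 3 and 4 are pooled in every outcome column and in the model covariate, so 3-4 results depend on the mix and the factor models may keep residual confounding by severity

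*Protocol*

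**What the plan says.** Protocol 6.3 sets the strata for the summaries: "Summary statistics will be generated for the cohort overall and by disease severity at baseline (2 vs 3/4 vs 5". Its list of factors for the Day 14 proportional odds model and the Day 28 Cox model repeats the grouping: "Baseline clinical status (2 vs 3/4 vs 5". SAP 8.1 presents mortality "globally and according to disease severity at baseline (ORDSC score 2 vs 3-4 vs 5". SAP 7.2, 8.2 and 9 and the columns of Tables 1 and 2 follow the same split.

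Elsewhere the documents keep the two pooled categories apart:

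- Protocol 2.3 defines category 3 as "Hospitalised, on non-invasive ventilation or high flow oxygen devices" and category 4 as "Hospitalised, requiring low flow supplemental oxygen".
- Table 1 in the SAP Appendix gives each its own baseline row, for example "3 - Hospitalized, on non-invasive ventilation or high flow oxygen devices".
- Protocol 2.2 and SAP section 3 set an objective that distinguishes low-flow from high-flow oxygen.

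Neither document explains the pooling or plans a sensitivity analysis that separates 3 from 4. The Protocol 6.3 factor list contains no NEWS 2, SpO2 or oxygen-support variable. The SAP does not specify the multivariable factor models.

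**The concern.** The scale ranks category 3 as worse than category 4, so their risks would be expected to differ. Three things then follow.

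- **Mix dependence.** A pooled 3-4 outcome is an average weighted by how many category 3 patients the sites happened to contribute. It does not carry over to a cohort with a different mix.
- **High-flow use.** SAP endpoint 4.1 reports low-flow and high-flow oxygen use by stratum. Category 3 can include patients already on high flow at baseline, whereas category 4 patients are on low flow and would reach high flow only by escalating. The pooled column mixes the two. This follows from the category definitions and needs no assumption about mortality.
- **Models.** A factor unevenly spread between 3 and 4 can take up part of the severity difference, and no other listed covariate measures respiratory support directly. Country is a natural example: Protocol section 3 plans a site survey of local standard of care and remdesivir protocols, so differing mixes by country are plausible.

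**Working it through.** **Inputs.** The plan has no figure to reproduce. Protocol 6.2 and SAP section 5 anticipate at least 450 cases, with no expected severity distribution or event rate. Every rate and share below is therefore an assumption.

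**1. Mix dependence.** Pooled mortality = s × m3 + (1 − s) × m4, where s is the category 3 share of the stratum and m3, m4 are the mortalities. For example, 0.30 × 25% + 0.70 × 10% = 14.5%.

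| Assumed m3 / m4 | s = 10% | s = 30% | s = 60% |
|---|---|---|---|
| 30% / 8% | 10.2% | 14.6% | 21.2% |
| 25% / 10% | 11.5% | 14.5% | 19.0% |
| 12% / 10% | 10.2% | 10.6% | 11.2% |

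The dependence is strong when the risks are far apart and slight when they are close.

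**2. Can the reader undo the pooling?** Table 1 will give s and Table 2 the pooled mortality. That is one equation in two unknowns. At s = 30%, the pairs 25%/10% and 30%/8% give 14.5% and 14.6%, which no study of this size could tell apart.

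**3. A factor with no effect, inside the 3-4 stratum.** Suppose 40% of carriers and 25% of non-carriers are category 3. Then RR = (0.40 × m3 + 0.60 × m4) / (0.25 × m3 + 0.75 × m4).

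- 25%/8%: 14.8 / 12.25 = 1.21
- 20%/10%: 14.0 / 12.5 = 1.12
- 15%/10%: 12.0 / 11.25 = 1.07

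If carriers and non-carriers have the same category 3 share, the ratio is exactly 1.

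Varying the imbalance, with HR ≈ ln(1 − r1) / ln(1 − r0), where r1 and r0 are the pooled risks in carriers and non-carriers, over the pairs 20%/10%, 25%/10% and 30%/8%:

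- shares 35% v 25%: HR 1.09 to 1.18
- shares 40% v 20%: HR 1.18 to 1.39
- shares 50% v 20%: HR 1.27 to 1.59

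These too are within-stratum values.

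**4. All strata contributing.** Categories 2 and 5 add no 3-versus-4 bias, so they dilute it. With equal numbers of carriers and non-carriers in each stratum, the Mantel-Haenszel ratio is the share-weighted sum of carrier risks over that of non-carrier risks. Assume stratum shares of 5-20% (category 2), 60-85% (3-4) and 10-20% (5), with mortality 30-40% in category 2 and 3% in category 5. For the 25%/8% pair:

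- shares 5/85/10, category 2 mortality 30%: (1.5 + 12.58 + 0.3) / (1.5 + 10.41 + 0.3) = 14.38 / 12.21 = 1.18
- shares 20/60/20, category 2 mortality 40%: (8 + 8.88 + 0.6) / (8 + 7.35 + 0.6) = 17.48 / 15.95 = 1.10

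So 1.21 becomes 1.10-1.18. In the same way, 1.12 becomes 1.06-1.10 and 1.07 becomes 1.03-1.06. Adjustment for other covariates could change these further. The Day 14 ordinal outcome was not quantified.

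**5. Is splitting feasible?** If 3-4 holds 60-80% of 450 and category 3 is 20-50% of that, category 3 has 54 (450 × 0.6 × 0.2) to 180 (450 × 0.8 × 0.5) patients, and category 4 has 135 to 288. With mortality of 25% and 10%, the exact 95% intervals are:

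- 54 v 216: 15.0-39.7% (14 deaths) and 6.5-15.0% (22 deaths)
- 180 v 180: 18.9-32.0% (45 deaths) and 6.0-15.3% (18 deaths)

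These are wide at the small end but still informative.

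**The case against.** The strongest reply is that this is a descriptive study. SAP section 2 tests no formal hypothesis, the models look for associated factors and name no causal contrast, and any cut of an ordinal scale loses something: category 3 itself joins non-invasive ventilation with high flow. Table 1 will publish the mix. Changing every three-group test would also be more work than adding a column, and it would thin small denominators such as re-admitted patients. Four levels would not even guarantee adjustment, because Protocol 6.3 keeps a variable only if its univariable P is below 0.10.

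Much of this stands. It argues for a light remedy that leaves the three-group tests alone, and for treating the retention rule as a separate matter. It does not justify the pooling: 3 and 4 are levels the plan itself defines and collects, no reason for merging them is given, and the published mix does not yield separate outcomes.

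A reader might infer more than the documents support:

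- *That 3-4 is the largest column.* No stratum sizes or expected distribution are given.
- *That the models are biased.* This requires both a risk difference between 3 and 4 and an uneven spread of the factor between them.
- *That 1.21 is the error in the planned Cox model.* It is a crude ratio within one stratum on assumed inputs.
- *That leaving out category 6 adds to these problems.* The scale includes "6. Hospitalised, not requiring supplemental oxygen - no longer requires ongoing medical care", and neither eligibility nor the Full Analysis Population excludes it, so such a patient would have no stratum or covariate level. Baseline is hospital admission, however, so the cell should be close to empty, and the gap causes neither mix dependence nor confounding.

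**Conclusion.** The concern holds in conditional form. Merging 3 with 4 in all outcome columns and in the Protocol 6.3 covariate is unexplained and has no sensitivity analysis. Mix dependence is certain arithmetically whenever the two risks differ; its size ranges from about one percentage point to about eleven over the assumed risks and shares of 10-60%. The blurring of baseline high-flow use with later escalation follows from the definitions.

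Residual confounding is possible, not established. With the 40% versus 25% imbalance it would be modest once all strata contribute; larger imbalances would give more, and an even spread gives none. It concerns the two models sketched in Protocol 6.3. This is a worthwhile, inexpensive improvement and does not invalidate the analysis.

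**What to change.** 1. In Protocol 6.3, enter baseline clinical status as 2, 3, 4, 5 in both models, and use the same coding in any SAP text that specifies them.
2. In SAP Table 2, add columns reporting outcomes for categories 3 and 4 separately. Keep the pooled 3-4 column and its three-group tests for comparability. The added columns can be descriptive.
3. As a minor clarification, state that any patient in category 6 at baseline is grouped with category 5 as not on oxygen.

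The data are already collected by category. The cost is one more degree of freedom per model (three instead of two for baseline status), two extra columns in Table 2, and wider intervals in those columns, widest for endpoints with small denominators such as outcome after re-admission.

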6.1 Timing of Analyses

An interim analysis is planned to be performed in June 2021.

The final analysis will be performed in July-September 2021.

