	Alert				
	Verbal				
	Pain				
	Unresponsive				

NEWS 2 score, median (IQR)						
	Low (score 0-4), n(%)					
	Medium (score 5-6)					
	High (score 7 or more)					
COVID Vaccination, n(%)						
Other treatment for COVID-19, n (%)						
	Corticosteroids					
	Tocilizimab/Sarilumab					
	Other COVID Treatment Related Drug					

Table 2. Primary and secondary outcomes

	Overall Total N=xxx	Ordinal Scale Category			
		Score of 2 N=xxx	Score of 3-4 N=xxx	Score of 5 N=xxx	P- value
Mortality over entire study period					
Number of deaths by Day 28					
Kaplan-Meier estimate of mortality by Day 28 – % (95% CI)					
Ordinal Scale at day 7 (± 1 day) – no. (%)					
1					
2					
3					
4					
5					
6					
7					
Ordinal Scale at day 14 (± 2 days) – no. (%)					
1					
2					
3					
4					
5					
6					
7					
Ordinal Scale at day 28 (± 2 days) – no. (%)					
1					
2					
3					
4					
5					
6					
7					
Disease severity assessed by NEWS 2 Score at 7 days					
Total N					
Mean NEWS 2 Score at days 7 (95% CI)					
Disease severity assessed by NEWS 2 Score at 14 days					
Total N					
Mean NEWS 2 Score at days 14 (95% CI)					
Disease severity assessed by NEWS 2 Score at 28 days					

Total N					
Mean NEWS 2 Score at days 28 (95% CI)					
SpO2>94% over first 7 days					
Number of SpO2>94% by Day 7					
Kaplan-Meier estimate of by Day 15 – % (95% CI)					
SpO2>94% over first 14 days					
Number of SpO2>94% by Day 14					
Kaplan-Meier estimate of SpO2>94 by Day 14 – % (95% CI)					
SpO2>94% over entire study period					
Number of SpO2>94% by Day 28					
Kaplan-Meier estimate of SpO2>94 by Day 28 – % (95% CI)					
Median time to SpO2>94% (95% CI) - days					
Oxygen therapy over entire study period (low or high flow)					
Number of oxygen therapy by Day 28					
Kaplan-Meier estimate of oxygen therapy by Day 28 – % (95% CI)					
Median duration on oxygen therapy (95% CI) - days					
Low flow oxygen therapy over entire study period					
Number of low flow oxygen therapy by Day 28					
Kaplan-Meier estimate of low flow oxygen therapy by Day 28 – % (95% CI)					
High flow oxygen therapy over entire study period					
Number of high flow oxygen therapy by Day 28					
Kaplan-Meier estimate of high flow oxygen therapy by Day 28 – % (95% CI)					
ICU admission over entire study period					
Number of ICU admission by Day 28					
Kaplan-Meier estimate of ICU admission by Day 28 – % (95% CI)					
Median duration spent in ICU (95% CI) - days					

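### The Day-14 and Day-28 prognostic models contain no calendar term, so any shift in outcome over the accrual period could be partly attributed to treatment timing or country

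*Protocol*

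**What the plan says.** **Accrual window.** Protocol 4.1 requires that cases be "Hospitalised after August 31st, 2020", and Protocol 6.1 describes the target population as "Adults with COVID-19 diagnosed and treated with Remdesivir after Aug 31st 2020". Both set a lower bound only. The outer limit has to be inferred from SAP 6.1, which plans an interim analysis in June 2021 and then states: "The final analysis will be performed in July-September 2021".

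**Change over time.** Under Protocol 3 each site or country is surveyed to "determine if standard protocols were/are in place for the use of Remdesivir and if/how the protocols changed over time". If Part 2 goes ahead, Protocol 6.1 takes its controls from patients "who were admitted in a 2 week time window of the cases". SAP Appendix Table 1 has a row for "COVID Vaccination, n" and rows for co-treatments, split by baseline severity.

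**Models.** Protocol 6.3 plans a proportional odds model for Day-14 status and a Cox model for "factors associated with survival at day 28 using Cox proportional hazards models". Nine candidates follow: "Participating country", age group, sex, geographic origin, baseline clinical status, body mass index, diabetes, high blood pressure, and time from symptom onset to treatment start (under 7 days against 7 or more). Those with univariable P < 0.10 go into the multivariable model.

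**Calendar time in the SAP.** Date of hospitalisation is the time origin for Day-28 death (8.1), duration of hospitalisation (8.2) and time from hospitalisation to remdesivir (9). The enrolment period is reported under 7.1. Group comparisons are by baseline severity. Neither the site survey nor any calendar variable enters an analysis as a covariate.

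**The concern.** Symptom-to-treatment time is the listed factor closest to practice, and country is the one most likely to be read as a difference in care. Both could vary with calendar time. A change in a local remdesivir protocol, which the survey asks about, could change when treatment starts, and countries may have contributed cases from different months. If mortality also moved over those months, a model without a calendar term would attribute part of the movement to timing or to country.

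The planned rules cannot correct this. The P < 0.10 screen applies only to listed variables, so period cannot enter by selection. Country does not stand in for period unless each country's cases fall in the same part of the window, and country is itself a factor to be interpreted. The plan controls for admission date in the conditional comparison with controls, but not in the case-only models of Part 1.

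**Working it through.** The plan gives no mortality rate, trend or power figure, so there is none to reproduce. All rates and shifts below are assumptions.

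**1. Length of the window.** From 1 September 2020 to 1 July 2021, the earliest start of the final analysis, is ten months. Allowing 28 days of follow-up brings the last admission to about nine months. This is an inference, since no cut-off is stated.

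**2. Spurious risk ratio for late treatment.** Take two equal halves of accrual, no true timing effect, late-starter shares l1 and l2 (7 days or more) and mortality m1 and m2.

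- Mortality in late starters = (l1·m1 + l2·m2)/(l1 + l2)
- Mortality in early starters = ((1−l1)·m1 + (1−l2)·m2)/(2 − l1 − l2)

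Moderate shift (late starters 50% to 30%, mortality 15% to 10%):

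- Late: (0.075 + 0.030)/0.80 = 13.1%
- Early: (0.075 + 0.070)/1.20 = 12.1%
- Risk ratio 1.09

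Strong shift (late starters 60% to 25%, mortality 18% to 9%):

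- Late: (0.108 + 0.0225)/0.85 = 15.4%
- Early: (0.072 + 0.0675)/1.15 = 12.1%
- Risk ratio 1.27

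If l1 = l2 the two mortalities are equal and the ratio is 1. If late starts rise as mortality falls, the bias reverses. With 30% to 50% and 15% to 10% it is 11.9% against 12.9%, a ratio of 0.92.

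**3. Cox model with and without a period term.** Simulation with 450 patients, a true timing hazard ratio (HR) of 1.00, two-sided 5% tests and 400 runs per row. The Monte Carlo error of a 5% rejection rate is √(0.05 × 0.95/400), about 1.1 percentage points.

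| Mortality | Share starting before day 7 | HR (rejections), no period | HR (rejections), with period |
|---|---|---|---|
| 15% to 15% | 40% to 60% | 1.010 (4.5%) | 1.010 (4.3%) |
| 15% to 12% | 40% to 60% | 1.066 (5.0%) | 1.016 (4.3%) |
| 15% to 10% | 40% to 60% | 1.075 (4.3%) | 0.984 (4.8%) |
| 20% to 10% | 40% to 60% | 1.160 (9.8%) | 1.009 (5.8%) |
| 20% to 10% | 30% to 70% | 1.359 (20.7%) | 1.016 (4.3%) |
| 20% to 10% | 50% to 50% | 0.986 (4.8%) | 0.986 (5.0%) |

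Mild and moderate shifts bias the estimate slightly without visibly raising the rejection rate. Only the larger shifts raise it. The simulated trend was a two-period step and the model adjusted for that same step.

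**4. Country, closed form.** Take two countries with no true difference and HR = ln(1−A)/ln(1−B), where A and B are their mortalities. If 60% and 40% of their cases fall in the early half and mortality goes from 15% to 10%, A = 13% and B = 12%, so HR = 1.09. If the shares are 80% and 20% and mortality goes from 20% to 10%, A = 18% and B = 12%, so HR = 1.55.

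**5. Room in the model.** Excluding country, the listed factors use 1 (age) + 1 (sex) + 2 (origin) + 2 (status) + 3 (BMI) + 1 (diabetes) + 1 (blood pressure) + 1 (timing) = 12 parameters. With an assumed six countries the total is 17 if everything passes the screen. At an assumed 10% to 20% mortality, 450 cases give 45 to 90 deaths.

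- As planned: 45/17 = 2.6 to 90/17 = 5.3 deaths per parameter
- With one linear term: 45/18 = 2.5 to 90/18 = 5.0
- With two period parameters: 45/19 = 2.4 to 90/19 = 4.7

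**The case against.** The strongest reply is that the study is exploratory, with no formal hypothesis, and looks only for association. The bias is conditional and, under moderate shifts, small beside sampling error. In the moderate case of step 2, with about 56 deaths, the apparent HR of 1.09 has a 95% interval of about 0.64 to 1.86 and the chance of a false positive is about 6% against 5%. In the strong case the HR is 1.29 (about 0.78 to 2.14) and the chance about 16%. The sums use no covariates, whereas the planned model may hold age, baseline status and country. A larger gap is that the SAP does not contain these prognostic models at all. Its proportional odds model only compares baseline-severity groups. The models are also already short of deaths.

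Much of this stands. It limits the size of the point and rules out flexible coding of period. It does not remove the point: the models exist to name prognostic factors, and a period term uses a date the study already needs.

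A reader might also infer more than the documents support:

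- **That the protocol expects care to change.** It asks whether and how remdesivir protocols changed. The two-week window belongs to a conditional Part 2, and the Table 1 rows are split by severity, not by time.
- **That admission date is unused for the cases.** It is the time origin for several SAP analyses. What is missing is its use as a covariate.
- **That accrual is unlimited.** Eligibility has no closing date, but the SAP analysis dates bound it in practice.

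**Conclusion.** The point holds as a conditional one. Neither document puts a calendar term in any prognostic model, while treatment timing and country are both candidates. If both outcome and timing (or country mix) shifted over the roughly nine or ten months, part of the trend would be attributed to them. Under the assumed shifts the spurious risk ratio for late treatment is 1.09 to 1.27. There is no material bias if timing does not shift, and the direction reverses if late starts rose while mortality fell.

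It would be too strong to say that the timing or country results will be confounded: the documents give no trend in mortality, timing or enrolment by country. Nor does the point touch the primary Kaplan-Meier estimate, which describes mortality in the cohort as enrolled. The change is worth making because it is cheap. Its absence does not invalidate the study.

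**What to change.** In Protocol 6.3, and in the SAP when these models are carried over:

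- Add admission date as one linear term, in weeks since 1 September 2020, kept in both the Day-14 and Day-28 models. Exempt it from the P < 0.10 screen and from the AIC choice between continuous and tertile coding, so that it stays at one parameter. Splines or quarters in the model are hard to support with 45 to 90 deaths.
- Exclude from this term, or flag, any admission date imputed under the partial-date rule in SAP 4.2, and report how many there are. A date known only as 2020 becomes 15 June 2020. That is 78 days (about 11 weeks) before the proposed origin and outside the study window.
- Tabulate Day-28 mortality and time to remdesivir by quarter of admission. This shows whether the two moved together. It also shows whether a straight line is a fair description, since a linear term would not remove a rise and fall.

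The cost is one parameter (deaths per parameter go from 2.6–5.3 to 2.5–5.0 under the assumptions above) and one table. Intervals for country would be somewhat wider if sites enrolled in short blocks. No new data are needed.
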